#### **8.1.4. Analysis of Time Data (time to the onset of event)**

Ninety-five percent confidence intervals for median, first quartile, and third quartile by the Kaplan-Meier method will be calculated. In addition, Kaplan-Meier plots will be prepared.

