3 STUDY SIZE

All the patients treated with this drug will be included in the all patient surveillance to be conducted for a specific period of time.

- Target number of cases: 600 cases
- Target number of cases observed: 300 cases treated for 12 weeks or longer (300 cases with Booklet 03 case report form)
(Cases who discontinued the drug before 12 weeks will also be included.)

[Rationale]

The incidence of all the adverse events included in the major investigation items of this study was 1.0% or higher in the drug group of the foreign phase 3 clinical study (304-WW Study). Assuming that the true incidence of an adverse event (particularly an adverse event included in the major investigation items) is 1.0%, 300 cases are required to observe at least 1 case with the event at a probability of at least 95%. The incidence of interstitial lung disease was 17.1% (14/82) in the multinational (Asian) phase 2 clinical study (2217-AP Study).

Assuming that the true incidence of interstitial lung disease is 17.1%, at least 40 cases with the disease can be observed at a probability of at least 95%.

Further, clinical study results showed that interstitial lung disease occurred on Week 4 after the start of the drug or later, and that, in rare cases, some adverse events had an increased incidence or delayed onset as the administration period was prolonged. Considering these results, it was decided to set a target that this study would include 300 cases treated with this drug for 12 weeks or longer.

Clinical study results showed that this drug could be continued for 12 weeks or longer in about 60% of the whole treated cases, with a discontinuance/drop-out rate at 12 weeks of about 40%. Considering that this study will be conducted under actual use condition, it is assumed that the discontinuance/drop-out rate at 12 weeks in this study will be increased by 10% to 50%. That is, it is assumed that this drug will be continued for 12 weeks or longer (the Booklet 03 case report form will be collected) in 50% of the cases included in this study.

Therefore, this surveillance was planned to register 600 cases to collect 300 cases treated with this drug for 12 weeks or longer. In addition, because cases which discontinue the drug before 12 weeks will be included in the study, the case report form will be collected from them to evaluate safety and effectiveness.

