### **2.1.2. Long-term Use Surveillance**

This study is a non-interventional study in a cohort of patients who were registered in the all patient surveillance and received this drug for unresectable or metastatic renal cell carcinoma for more than 24 weeks.

*Among the patients registered and treated in the all patient surveillance, those to be continuously treated with this drug for more than 24 weeks will be included in this study. That is, the target number of cases to be registered in the all patient surveillance is 600 (rationale stated in the protocol of the all patient surveillance) and those to be continuously treated for more than 24 weeks will be registered again in this study. Therefore, no definite target number of cases is set for this study. However, the expected number of cases to be registered in this study is shown below and considered as the target number of cases to be registered.*

*Expected number of cases: about 120 cases*

*[Rationale]*

*The expected number of cases to be registered in this study is described. In the clinical trials, (304-WW and 2217-AP Studies), about 35% of the subjects could be continuously treated for 24 weeks or longer, with a discontinuance/drop-out rate at 24 weeks being about 65%. Considering that the all patient surveillance will be conducted under actual use condition, and that it is necessary to re-register from all patient surveillance to this study, it is assumed that the discontinuance/drop-out rate at 24 weeks in the all patient surveillance will be further increased by 15% to 80%. That is, it is assumed that 20% of the cases included in the all patient surveillance will be registered in this study after the completion of the all patient surveillance. It is therefore expected that about 120 cases will be registered in this study when 600 cases will be registered in the all patient surveillance. However, the actual number of cases registered may be different from the expected number because it depends on the conditions and results of the all patient surveillance.*

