The number of patients with CTCAE Grade  $\geq 3$  adverse reactions and the incidence of CTCAE Grade  $\geq 3$  adverse reactions will be tabulated by SOC and PT by category shown below. •Further tabulation of serious adverse reactions” will be followed for categories.

- Seriousness;
- Known/unknown;
- Outcome;
- Timing of initial onset;
- Intervention;
- Administration of this drug;
- Duration of treatment;
- Total dose.

- **Further tabulation of adverse events**

The number of patients with adverse events and the incidence of adverse events will be tabulated by SOC and PT by category shown below. “• Further tabulation of serious adverse reactions” will be followed for categories.

- CTCAE Grade.

- **Further tabulation of unknown adverse reactions**

The number of patients with unknown adverse reactions and the incidence of unknown adverse reactions will be tabulated by SOC and PT by category shown below. “•Further tabulation of serious adverse reactions” will be followed for categories.

- Outcome.

- **Cumulative incidence of adverse reactions**

The cumulative incidence of adverse reactions will be graphically presented with the time to onset on the horizontal axis.

The cumulative incidence will be graphically presented in the same manner for interstitial lung disease, diabetes mellitus/hyperglycemia, hypercholesterolemia/hyperlipidemia, infection, mucositis-related adverse events, and skin disorder among major investigation items.

- **Cumulative incidence of CTCAE Grade  $\geq 3$  adverse reactions**

The cumulative incidence of CTCAE Grade  $\geq 3$  adverse reactions will be graphically presented with the time to onset on the horizontal axis.

The cumulative incidence will be graphically presented in the same manner for interstitial lung disease, diabetes mellitus/hyperglycemia, hypercholesterolemia/hyperlipidemia, infection, mucositis-related adverse events, and skin disorder among major investigation items.

- **Incidence of adverse reactions by patient demographic**

The number of patients with adverse reactions and the incidence of adverse reactions will be tabulated by item listed in “[Section 10.1.1. Patient demographics to be used to evaluate safety and efficacy.](#)”

Fisher’s exact test will be performed for nominal scale data and Cochran-Armitage test (exact method) for ordered scale data.

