11. Complications.

The number of patients with adverse reactions, serious adverse reactions, and CTCAE Grade  $\geq 3$  adverse reactions and the incidence of these adverse reactions will be calculated by SOC and PT.

For items using reference values, results using corporate reference values will be tabulated in addition to results using institutional reference values.

- **Major investigation items**

The number of patients with adverse reactions falling under major investigation items and the incidence of these adverse reactions will be calculated by SOC and PT. The number of patients with adverse events and the incidence of adverse events will be tabulated in the same manner.

The same tabulation will be performed for each of the following items.

1. Interstitial lung disease.
2. A wide range of related events suspected of interstitial lung disease.
3. Dyspnea.
4. Diabetes mellitus/hyperglycemia.
5. Hypersensitivity reaction.
6. Diarrhea.
7. Hypophosphatemia.
8. Hypokalemia.
9. hypercholesterolemia/hyperlipidemia.
10. Infection.
11. Intracerebral hemorrhage.
12. Abnormality in wound healing.
13. Mucositis-related adverse events.
14. Skin disorder.
15. Acute renal failure.
16. Gastrointestinal perforation.

- **Further tabulation of interstitial lung disease**

The number of patients with adverse reactions and adverse events of interstitial lung disease and the incidences of these adverse reactions and adverse events will be tabulated by presence or absence of past or present history of lung disease and presence or absence of abnormal imaging findings at the initiation of treatment by category shown below.

- Seriousness;
- Clinical symptoms;
- Severity (CTCAE Grade);
- Time from the initiation of treatment to initial onset (weeks);
- Cumulative duration (weeks);
- Imaging findings suspected of interstitial lung disease.

The worst CTCAE Grade and treatment effect will be tabulated by presence or absence of treatment of interstitial lung disease.

The outcome in patients in whom interstitial lung disease was CTCAE Grade 1 at onset will be tabulated by status (continued/discontinued) of treatment.

The list of the course of interstitial lung disease and the list of the time course of CTCAE Grade will be prepared.

Graphs of time from the initiation of treatment to initial onset (weeks), outcome, and administration of this drug will be prepared by CTCAE Grade at onset. Graphs will be prepared in the same manner by maximum CTCAE Grade.

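### The cumulative-incidence graphs of adverse reactions have no named estimator beyond Kaplan-Meier and no rule for death; drawn as 1-KM with deaths censored, they would read too high

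*SAP*

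**What the plan says.** SAP 8.1.4 is the only visible section on time-to-event methods, and its heading refers to time to the onset of an event. It specifies Kaplan-Meier plots and: "Ninety-five percent confidence intervals for median, first quartile, and third quartile by the Kaplan-Meier method will be calculated".

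SAP 8.2.6 asks for the time course of reactions: "The cumulative incidence of adverse reactions will be graphically presented with the time to onset on the horizontal axis". It continues: "The cumulative incidence will be graphically presented in the same manner for interstitial lung disease", and lists five further major items (diabetes/hyperglycaemia, hypercholesterolaemia/hyperlipidaemia, infection, mucositis-related events, skin disorder). The same set is requested for Grade 3 or higher reactions. No estimator, censoring rule or treatment of death is given for these graphs. Censoring is defined only for duration of treatment (SAP 6.1) and progression-free survival (SAP 6.2). SAP 7, on missing data, is marked not applicable.

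Separately, SAP 8.2.6 provides plain incidence tables: "The number of patients with adverse reactions falling under major investigation items and the incidence of these adverse reactions will be calculated by SOC and" preferred term.

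On follow-up, Protocol 5.4 observes adverse events to Week 24, or to Day 28 after an earlier discontinuation. Protocol 6.8 ends reporting when a new treatment starts. Protocol 6.7 lists death, with its date, as a reason for discontinuation. SAP 8.2 pools the all patient surveillance with the long-term surveillance, which runs to Week 96.

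**The concern.** The population has metastatic or unresectable renal cell carcinoma, and death during observation is foreseen. Kaplan-Meier with deaths censored treats a patient who died without the reaction as someone who could still have developed it later. Its complement therefore describes risk in a hypothetical setting without death. The share of treated patients who actually develop the reaction is smaller whenever deaths occur before onset.

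The onset state of adverse events and of ILD is the subject of objectives 2 and 3, and the long-term surveillance looks at ILD over Weeks 25 to 96. These graphs are the main display of time course. Under constant hazards the gap between 1-KM and the actual cumulative incidence widens with follow-up, so it would be largest in the period the long-term question concerns. Any Kaplan-Meier quartiles of time to onset would be affected too: the curve would reach a given level too early.

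**Working it through.** **Inputs from the documents**

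- ILD incidence (Protocol 3): "The incidence of interstitial lung disease was 17.1% (14/82"), that is, 14/82 = 17.07%.
- Exit by Week 12 (Protocol 3): "it is assumed that the discontinuance/drop-out rate at 12 weeks in this study will be increased by 10% to 50" per cent.
- Exit by Week 24 (SAP 2.1.2): "it is assumed that the discontinuance/drop-out rate at 24 weeks in the all patient surveillance will be further increased by 15% to 80" per cent. This figure also allows for failure to re-register in the long-term surveillance.
- Death rate: none given.

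**The plan's own figures.** The documents state no Kaplan-Meier or cumulative-incidence value. Their sample-size figures reproduce: P(at least 1 event in 300 at 1.0%) = 1 − 0.99^300 = 0.951, and P(at least 40 ILD cases in 300 at 17.1%) = 0.968 by the exact binomial. Neither is affected by this point.

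**Model for the size of the effect.** Assume constant hazards, and treat non-fatal exit as independent censoring.

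- Exit hazard: e = ln(2)/12 = 0.0578 per week. This gives 50% exit at Week 12 and 1 − 0.5² = 75% at Week 24.
- Death hazard: d = s × e, where s is the assumed share of exits that are deaths.
- True cumulative incidence with death competing: AJ(24) = λ/(λ+d) × [1 − exp(−24(λ+d))].
- What 1-KM shows: 1 − exp(−24λ).

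For each s, solve for the reaction hazard λ that makes AJ(24) = 0.171, then read off 1-KM:

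| s (assumed) | d per week | λ per week | 1-KM at Week 24 | Excess over 17.1% |
|---|---|---|---|---|
| 0% | 0 | 0.00781 | 17.1% | 0 |
| 10% | 0.00578 | 0.00841 | 18.3% | 1.2 points |
| 25% | 0.01444 | 0.00935 | 20.1% | 3.0 points |
| 50% | 0.02888 | 0.01108 | 23.3% | 6.2 points |

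For scale, s = 50% means about 0.5 × 75% = 37.5% of patients leaving through death by Week 24. That row is an upper bound for illustration, not an expectation.

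**Sensitivity to calibration.** The 17.1% is a crude proportion, so it can instead be taken as the share of patients in whom ILD is observed after exits have removed others from view. With a piecewise-constant exit hazard fitted to 50% and 80% at Weeks 12 and 24, and ILD possible from Week 0, 1-KM is 31.1%. Aalen-Johansen gives 30.1%, 29.1%, 27.2%, 25.5% and 22.5% for s = 5%, 10%, 20%, 30% and 50%. The excess is 1.1, 2.1, 3.9, 5.6 and 8.6 points (from unrounded values). With the clinical-trial exit rates (40% and 65%) it is 0.6 to 5.6 points over the same range of s. The Protocol says "interstitial lung disease occurred on Week 4 after the start of the drug or later"; starting the ILD hazard at Week 4 gives 1.4 to 11.7 points at plan rates and 0.8 to 7.2 points at trial rates. With s = 0 the excess is zero in every case.

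Both calibrations ignore the 28-day observation window after stopping and assume that leaving is unrelated to ILD risk.

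**The case against.** The strongest reply is that SAP 8.2.6 never says its graphs are 1-KM. Kaplan-Meier has proper uses in this plan, for progression-free survival and duration of treatment, and the confidence-interval sentence in 8.1.4 entered in version 3.0 together with progression-free survival. Part of the analysis text is blacked out and may hold more detail. The study is also not confirmatory (SAP 4), and no decision rule hangs on the curves.

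The first part stands to this extent: use of 1-KM is an inference. It is the natural one, because 8.1.4 is headed time to onset and offers nothing else, and the change log shows the section was added in version 2.0, before progression-free survival entered the plan. Duration of treatment was added in that same version, so the log supports this reading without proving it.

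A reader might go further in three ways that the documents do not support.

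- That the graphs are certain to overstate incidence. The estimator is not named. A crude count over all treated patients would tend to err low instead, because patients leave observation.
- That heavy attrition by itself inflates the curves. Non-fatal discontinuation is ordinary censoring. It biases 1-KM only if it is informative, in a direction the documents do not settle.
- That the reported ILD incidence is wrong throughout. The tables by system organ class and preferred term are simple proportions, and the risk-factor comparisons use Fisher and Cochran-Armitage tests. None of these relies on Kaplan-Meier.

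**Conclusion.** The point holds in conditional form. The visible plan gives Kaplan-Meier as the only method for time to onset and is silent on death in the cumulative-incidence graphs. If deaths are censored and 1-KM is plotted, the graphs would overstate cumulative incidence. For a true 24-week ILD incidence of 17.1%, the excess is about 1.2, 3.0 or 6.2 points if deaths are 10%, 25% or 50% of exits. Over both calibrations and the exit rates tried, it ranges from 0.6 to 11.7 points for death shares of 5% to 50%, and it is zero without deaths. Every non-zero figure rests on an assumed death share, on the assumed hazard shapes, and on non-fatal exit being unrelated to ILD. The effect is confined to the time-course graphs and any Kaplan-Meier quartiles of time to onset. It is worth correcting because a better estimator is available at little cost.

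**What to change.** In SAP 8.1.4 and 8.2.6, state that cumulative incidence of adverse reactions (all, Grade 3 or higher, and the six major items) is estimated by the Aalen-Johansen method, with death without the reaction as a competing event. State that other patients without the reaction are censored at the end of adverse-event observation: Week 24 or the end of long-term follow-up, 28 days after discontinuation, or the start of a new treatment, whichever comes first. Show numbers at risk under each graph. Keep Kaplan-Meier for progression-free survival and duration of treatment.

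The cost is a small programming change. Dates of onset, administration and death are already collected (Protocol 6.2, 6.7 and 6.8); the start of a new treatment should be confirmed as available in the data. The curves will lie slightly below 1-KM.

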### **8.2. Statistical Analyses**

Unless otherwise specified, data from the all patient surveillance and data from the long-term use surveillance will be tabulated and analyzed together.

#### **8.2.1. Appendix Form 3 (list of the summary of included patients)**

Appendix Form 3 (list of the summary of included patients) will be prepared for registered patients.

#### **8.2.2. Appendix Form 2 (list of the onset state of adverse reactions and infections)**

Appendix Form 2 (list of the onset state of adverse reactions and infections) will be prepared for patients included in the safety analysis.

### **8.2.3. Appendix Form 10 (list of the onset state of serious adverse events)**

Appendix Form 10 (list of the onset state of serious adverse events) will be prepared for patients included in the safety analysis.

### **8.2.4. Summary of Patients**

- Number of study sites and number of patients by type of establisher.**

The number and percentage of study sites and the number and percentage of patients will be tabulated by type of establisher in patients for whom the case report form was collected.

In addition, the mean, minimum, and maximum of the number of patients per site will be tabulated.

University hospitals, national hospitals established by the Ministry of Health, Labour and Welfare, prefectural and municipal hospitals, public organizations, and hospitals and clinics other than the above 4 types established by corporations and individuals

- Composition of patients.**

The number of registered patients, patients for whom the case report form was collected, patients included in the safety analysis, and patients included in the efficacy analysis, and the number of patients excluded from registration, patients for whom the case report form was not collected, patients excluded from the safety analysis, and patients excluded from the efficacy analysis, and the number of patients by reason will be tabulated in registered patients.

- Status of discontinuation and dropout.**

The number of patients will be tabulated by whether the study was discontinued and reason for discontinuation by volume of case report form in the safety analysis set.

Similarly, the number of patients will be tabulated by whether the study was discontinued and reason for discontinuation by duration of treatment.

- List of excluded patients and reasons for exclusion.**

The list of patients excluded from the safety analysis, patients excluded from the efficacy analysis, and reasons for exclusion will be prepared.

### **8.2.5. Patient Demographics and Treatment History**

- Patient demographics**

The frequency tabulation of the following patient demographics and baseline characteristics will be performed in the safety analysis set and efficacy analysis set. Basic statistics will be tabulated for continuous scales.

For items using reference laboratory test values, results using corporate reference values will be tabulated separately from results using institutional reference values as necessary.

[Demographic and other baseline characteristics]:

- Sex [male, female];
- Age (continuous data);
- Age [ $<15$  years,  $\geq 15$  to  $<65$  years,  $\geq 65$  years];
- Age [ $<45$  years,  $\geq 45$  to  $<55$  years,  $\geq 55$  to  $<65$  years,  $\geq 65$  to  $<75$  years,  $\geq 75$  to  $<85$  years,  $\geq 85$  years];
- Age [ $<15$  years,  $\geq 15$  years];
- Age [ $<65$  years,  $\geq 65$  years];
- Body surface area ( $m^2$ ) [ $<1.2$ ,  $\geq 1.2$  to  $<1.4$ ,  $\geq 1.4$  to  $<1.6$ ,  $\geq 1.6$  to  $<1.8$ ,  $\geq 1.8$ ];
- Height (continuous data);
- Weight (continuous data);
- Body mass index (BMI) (continuous data);
- BMI [low weight ( $< 18.5$ ), ordinary weight ( $\geq 18.5$  to  $<25.0$ ), Obese Class I ( $\geq 25.0$  to  $<30.0$ ), Obese Class II ( $\geq 30.0$  to  $<35.0$ ), Obese Class III ( $\geq 35.0$  to  $<40.0$ ), Obese Class IV ( $\geq 40.0$ )];
- Inpatient/outpatient status [inpatient, outpatient];
- Past medical history [absent, present];

- Past history of lung disease [absent, present];
- Past history of interstitial lung disease [absent, present];
- Past history of hepatitis B, tuberculosis, and herpes zoster [absent, present];
- Past history of diabetes mellitus [absent, present];
- Complications [absent, present];
- Comorbid lung disease [absent, present];
- Comorbid interstitial lung disease [absent, present];
- Comorbid hepatitis B, tuberculosis, and herpes zoster [absent, present];
- Comorbid diabetes mellitus [absent, present];
- Hepatic dysfunction [absent, present];
- Severity of hepatic dysfunction [mild, moderate, severe];
- Renal dysfunction [absent, present];
- Severity of renal dysfunction [mild, moderate, severe];
- ECOG Performance Status [0, 1, 2, 3, 4];
- Karnofsky Performance Status [10-20, 30-40, 50-60, 70-80, 90-100];
- Risk classification (Memorial Sloan Kettering Cancer Center [MSKCC] Risk) [good (0 of 5 items), intermediate (1 to 2 of 5 items), poor (3 to 5 of 5 items)];
- Risk classification (Modified Risk) [low risk (0 to 2 of 6 items), high risk (3 to 6 of 6 items)];
- Risk classification, time from the diagnosis of renal cell carcinoma to the initial systemic chemotherapy <1 year [yes, no];
- Risk classification, Karnofsky Performance Status  $\leq 70$  [yes, no];
- Risk classification, hemoglobin < institutional lower reference limit [yes, no];

- Risk classification, adjusted calcium  $>10$  mg/dL [yes, no];
- Risk classification, LDH  $>1.5$ -fold of institutional upper reference limit [yes, no];
- Risk classification, number of metastatic foci  $\geq 2$  [yes, no].

[Characteristics of target disease and prior treatment history]:

- Target disease [unresectable or metastatic renal cell carcinoma, others];
- Presence or absence of metastasis (at the initiation of treatment) [absent, present];
- Number of metastatic foci (at the initiation of treatment) [0, 1,  $\geq 2$ ];
- Site of metastasis (at the initiation of treatment) [lung, liver, bone, brain, others];
- Histopathologic diagnosis [clear cell, non-clear cell, not performed];
- Histopathologic diagnosis (description) [clear cell, granule cell, chromophobe cell, spindle cell, cyst-associated renal cell, cyst-derived renal cell, cystic renal cell, papillary renal cell, others];
- Disease stage (at the diagnosis of target disease) [STAGE 0, STAGE 1, STAGE 2, STAGE 3, STAGE 4];
- Duration of illness [ $\geq 0$  to  $\leq 12$  months,  $\geq 13$  to  $\leq 24$  months,  $\geq 25$  to  $\leq 48$  months,  $\geq 49$  months];
- Prior treatment history (history of surgery: primary focus) [absent, present];
- Prior treatment history (history of surgery: nephrectomy) (partial or total resection of primary focus) [absent, present];
- Prior treatment history (history of surgery: metastatic focus) [absent, present];
- Prior treatment history (history of radiation therapy) [absent, present];
- Prior treatment history (history of non-drug therapy) [absent, present];
- Prior treatment history (drug therapy) [absent, present];

- Prior treatment history (description of drug therapy) [IFN- $\alpha$ , IL-2, Sutent, Nexavar, Afinitor, others].

[Criteria for the proper use of this drug]:

- Whether criteria for proper use are met [yes, no];
- Eastern Cooperative Oncology Group Performance Status (ECOG PS) 0 to 2 [yes, no];
- Neutrophil count  $\geq 1.5 \times 10^9/L$  ( $1500/\text{mm}^3$ ) [yes, no];
- Hemoglobin  $\geq 8 \text{ g/dL}$  [yes, no];
- Platelet count  $\geq 100 \times 10^9/L$  ( $10 \times 10^4/\text{mm}^3$ ) [yes, no];
- Serum creatinine  $\leq 1.5$ -fold of institutional upper reference limit [yes, no];
- BUN  $\leq 1.5$ -fold of institutional upper reference limit [yes, no];
- Total bilirubin  $\leq 1.5$ -fold of institutional upper reference limit [yes, no];
- AST/ALT  $\leq 3$ -fold of institutional upper reference limit ( $\leq 5$ -fold of institutional upper reference limit if liver metastasis is observed) [yes, no];
- Chest CT normal [yes, no];
- Chest X-ray normal [yes, no];
- Measurement of markers for interstitial lung disease such as KL-6, normal [yes, no];
- Pulmonary function test (PFT) normal [yes, no];
- Measurement of oxygen saturation normal [yes, no];
- Total cholesterol  $\leq 350 \text{ mg/dL}$  ( $9.9 \text{ mmol/L}$ ) [yes, no];
- Triglyceride  $\leq 400 \text{ mg/dL}$  ( $4.56 \text{ mmol/L}$ ) [yes, no];
- Hemoglobin A1C  $< 10\%$  [yes, no];

- Fasting blood glucose  $\leq$ 1.5-fold of institutional upper reference limit [yes, no].

[Concomitant therapies and other background information]:

- Concomitant therapy (drug therapy) [absent, present];
- Concomitant therapy (non-drug therapy) [absent, present];
- History of smoking [absent, present];
- Family history of diabetes mellitus [absent, present];
- History of pulmonary surgery [absent, present];
- History of steroid use [absent, present];
- History of occupational and environmental exposure to asbestos, pneumoconiosis-producing dusts, etc. [absent, present];
- History of administration of highly concentrated oxygen for treatment of respiratory disease [absent, present];
- Drug allergies [absent, present];
- Allergies other than drug allergies [absent, present].

Corporate reference value

Test parameter	Unit	Lower limit		Upper limit	
		Male	Female	Male	Female
Hemoglobin	g/dL	13.5	11.3	17.6	15.2
White blood cell count	/ $\mu$ L	3900	3500	9800	9100
White blood cell differential/neutrophil	%	27	28	87	90
Platelet count	$\times 10^4/\mu$ L	13.1	13	36.2	36.9
AST	IU/L	7		38	

Test parameter	Unit	Lower limit		Upper limit	
		Male	Female	Male	Female
ALT	IU/L	4		44	
Total bilirubin	mg/dL	0.2		1	
Total cholesterol	mg/dL	130		219	
Triglyceride	mg/dL	30		150	
Fasting blood glucose	Mg/dL	60		110	
HbA1C	%	4.3		5.8	
BUN	mg/dL	8		20	
Serum creatinine	mg/dL	0.8	0.6	1.2	0.9
K	mEq/L	3.7		4.8	
P	mg/dL	2.5		4.5	
	mmol/L	0.8		1.4	
CRP	mg/dL			0.3	
SpO2	%	95		100	
KL-6	U/mL			500	
SP-D	ng/mL			<110	
SP-A	ng/mL	15		34.2	
LDH	IU/L	106		220	
Serum albumin	g/dL	3.8		5.5	
Serum calcium	mg/dL	8.5		10.2	
	mEq/L	4.2		5.1	
	mmol/L	2.1		2.5	
ALP	IU/L	106		345	

- **Past medical history**

The number and percentage of patients will be tabulated by past medical history in the safety analysis set.

- **Complications**

The number and percentage of patients will be tabulated by complication in the safety analysis set.

- **Concomitant medications**

The number and percentage of patients will be tabulated by concomitant medication in the safety analysis set.

- **Non-drug therapies**

The number and percentage of patients will be tabulated by non-drug therapy in the safety analysis set.

- **Prior medications**

The number and percentage of patients will be tabulated by prior medication in the safety analysis set.

- **Other reasons for use**

The list of other reasons for use of this drug will be prepared in the safety analysis set.

- **Status of exposure to this drug**

The frequency distribution of the following status of exposure to this drug will be tabulated in the safety analysis set and efficacy analysis set. Basic statistics will be tabulated for continuous scales.

[Status of exposure to this drug]:

- Dose at initiation [ $>0$  to  $\leq 5$  mg,  $>5$  to  $\leq 10$  mg,  $>10$  to  $\leq 15$  mg,  $>15$  to  $\leq 20$  mg,  $>20$  to  $\leq 25$  mg,  $>25$  mg];

- Duration of treatment (weeks) [ $>0$  to  $\leq 8$  weeks,  $>8$  to  $\leq 16$  weeks,  $>16$  to  $\leq 24$  weeks,  $>24$  to  $\leq 48$  weeks,  $>48$  to  $\leq 72$  weeks,  $>72$  to  $\leq 96$  weeks,  $>96$  weeks];
- Total dose (mg) [ $>0$  to  $\leq 200$  mg,  $>200$  to  $\leq 400$  mg,  $>400$  to  $\leq 600$  mg,  $>600$  to  $\leq 1200$  mg,  $>1200$  to  $\leq 1800$  mg,  $>1800$  to  $\leq 2400$  mg,  $>2400$  mg];
- Dose intensity (mg/week) [ $>0$  to  $\leq 10$  mg,  $>10$  to  $\leq 15$  mg,  $>15$  to  $\leq 20$  mg,  $>20$  to  $\leq 25$  mg,  $>25$  to  $\leq 30$  mg,  $>30$  mg];
- Relative dose intensity [ $>0.0$  to  $\leq 0.4$ ,  $>0.4$  to  $\leq 0.6$ ,  $>0.6$  to  $\leq 0.8$ ,  $>0.8$  to  $\leq 1.0$ ,  $>1.0$  to  $\leq 1.2$ ,  $>1.2$ ];
- Presence or absence of temporary discontinuation of treatment [absent, present];
- Reason for temporary discontinuation of treatment [adverse event, others];
- Presence or absence of dose reduction [absent, present];
- Reason for dose reduction [adverse event, others].

- **Duration of observation**

The frequency distribution of the duration of observation will be tabulated in the safety analysis set and efficacy analysis set. In addition, basic statistics will be tabulated.

- **Status of implementation of chest CT**

The frequency distribution of the status of implementation of chest CT will be tabulated in the safety analysis set.

The same tabulation will be performed in patients in whom measurement was performed in all timing categories.

